### 3.3 Registration – Inclusion Criteria

- 3.31 Histologic confirmation of Stage III melanoma, as defined by the American Joint Committee on Cancer, 8th revised edition.
- 3.32 Arms A and B only: Documentation of BRAFV600 mutation status in melanoma tumor tissue (archival or newly obtained) through use of a CLIA-approved clinical mutation test.
- 3.33 Surgically resectable disease, as determined by a melanoma surgical oncologist.
- 3.34 Eastern Cooperative Oncology Group (ECOG) Performance Status of 0 or 1 (See [Appendix I](#)).
- 3.35 Life expectancy  $\geq 26$  weeks.
- 3.36 The following laboratory values obtained  $\leq 14$  days prior to registration:
  - Absolute neutrophil count (ANC)  $\geq 1500/\text{mm}^3$
  - Platelet count  $\geq 100,000/\text{mm}^3$
  - Hemoglobin  $\geq 9.0$  g/dL
  - Direct bilirubin  $\leq$  institutional upper limit of normal (ULN)
  - Aspartate transaminase (AST) and alanine transaminase (ALT)  $\leq 2 \times$  ULN
  - Alkaline phosphatase  $< 2.5 \times$  ULN
  - Creatinine  $\leq 1.5 \times$  ULN or creatinine clearance (CrCl)  $\geq 45$  mL/min on the basis of measured CrCl from a 24-hour urine collection or Cockcroft-Gault glomerular filtration rate estimation:  

$$\text{CrCl} = \frac{(140 - \text{age}) \times (\text{weight in kg})}{72 \times (\text{serum creatinine in mg/dL})} \quad (\times 0.85 \text{ if female})$$
- 3.37 Arms A and B only: LVEF  $\geq 50\%$  or institutional LLN  $\leq 6$  months prior to registration.
- 3.38 Arms A and B only: Average QTc  $\leq 450$  ms on triplicate 12 lead ECG  $\leq 28$  days prior to registration.  
NOTE: QTc intervals will be corrected using Fridericia's formula (Fridericia 1920)
- 3.39a Negative pregnancy test done  $\leq 7$  days prior to registration, for persons of childbearing potential only.
- 3.39b For persons of childbearing potential: agreement to remain abstinent (refrain from heterosexual intercourse) or use a contraceptive method with a failure rate of  $< 1\%$  per year during the treatment period and for 6 months after the last dose of study treatment.
- 3.39c For persons able to father a child: agreement to remain abstinent (refrain from heterosexual intercourse with a person of childbearing potential) or use contraceptive measures, and agreement to refrain from donating sperm during the treatment period and for 6 months after the last dose of study treatment.
- 3.39d Provide written informed consent.

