## 9.8 Contraception

The treatments used in this study may have adverse effects on a fetus in utero. Furthermore, it is not known if the treatment has transient adverse effects on the composition of sperm.

For this trial, male patients will be considered to be of non-reproductive potential if they have azoospermia (whether due to having had a vasectomy or due to an underlying medical condition).

Female patients will be considered of non-reproductive potential if they are either:

(1) postmenopausal (defined as at least 12 months with no menses without an alternative medical cause; in women <45 years of age a high follicle stimulating hormone (FSH) level in the postmenopausal range may be used to confirm a post-menopausal state in women not using hormonal contraception or hormonal replacement therapy. In the absence of 12 months of amenorrhea, a single FSH measurement is insufficient.);

OR

(2) have had a hysterectomy and/or bilateral oophorectomy, bilateral salpingectomy or bilateral tubal ligation/occlusion, at least 6 weeks prior to screening;

OR

(3) have a congenital or acquired condition that prevents childbearing.

Female and male patients of reproductive potential must agree to avoid becoming pregnant or impregnating a partner, respectively, while receiving study drug and for 5 months after the last dose of study drug by complying with one of the following:

(1) practice abstinence† from heterosexual activity;

OR

(2) use (or have their partner use) acceptable contraception during heterosexual activity.

Acceptable methods of contraception are‡:

Single method (one of the following is acceptable):

- intrauterine device (IUD)
- vasectomy of a female subject's male partner
- contraceptive rod implanted into the skin

Combination method (requires use of two of the following):

- diaphragm with spermicide (cannot be used in conjunction with cervical cap/spermicide)
- cervical cap with spermicide (nulliparous women only)
- contraceptive sponge (nulliparous women only)
- male condom or female condom (cannot be used together)

 La Rosée P. Treatment of hemophagocytic lymphohistiocytosis in adults. Hematology Am Soc Hematol Educ Program 2015;1:190–6.

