- hormonal contraceptive: oral contraceptive pill (estrogen/progestin pill or progestin-only pill), contraceptive skin patch, vaginal contraceptive ring, or subcutaneous contraceptive injection

†Abstinence (relative to heterosexual activity) can be used as the sole method of contraception if it is consistently employed as the subject's preferred and usual lifestyle and if considered acceptable by local regulatory agencies and ERCs/IRBs. Periodic abstinence (e.g., calendar, ovulation, sympto-thermal, post-ovulation methods, etc.) and withdrawal are not acceptable methods of contraception.

‡If a contraceptive method listed above is restricted by local regulations/guidelines, then it does not qualify as an acceptable method of contraception for patients participating at sites in this country/region.

Patients should be informed that taking the study medication may involve unknown risks to the fetus (unborn baby) if pregnancy were to occur during the study. In order to participate in the study patients of childbearing potential must adhere to the contraception requirement (described above) from the day of study medication initiation (or 14 days prior to the initiation of study medication for oral contraception) throughout the study period up to 5 months after the last dose of trial therapy. If there is any question that a patient of childbearing potential will not reliably comply with the requirements for contraception, that patient should not be entered into the study.

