## 10.5 Other Required Reporting

### 10.51 Unanticipated Problems Involving Risks to Subjects or Others (UPIRTSOS)

Unanticipated Problems Involving Risks to Subjects or Others (UPIRTSOS) in general, include any incident, experience, or outcome that meets **all** of the following criteria:

- Unexpected (in terms of nature, severity, or frequency) given (a) the research procedures that are described in the protocol-related documents, such as the IRB-approved research protocol and informed consent document; and (b) the characteristics of the subject population being studied;
- Related or possibly related to participation in the research (in this guidance document, possibly related means there is a reasonable possibility that the incident, experience, or outcome may have been caused by the procedures involved in the research); and
- Suggests that the research places subjects or others at a greater risk of harm (including physical, psychological, economic, or social harm) than was previously known or recognized.

Some unanticipated problems involve social or economic harm instead of the physical or psychological harm associated with adverse events. In other cases, unanticipated problems place subjects or others at increased *risk* of harm, but no harm occurs.

Note: If there is no language in the protocol indicating that pregnancy is not considered an adverse experience for this trial, and if the consent form does not indicate that subjects should not get pregnant/impregnate others, then any pregnancy in a subject/patient or a male patient's partner (spontaneously reported) which occurs during the study or within 120 days of completing the study should be reported as a UPIRTSO.

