#### **f. Pregnancy**

If a female subject becomes pregnant while receiving the atezolizumab and/or tiragolumab and/or vemurafenib and/or cobimetinib or within 90 days after the last dose of vemurafenib and/or cobimetinib or within 5 months after the last dose of atezolizumab and/or tiragolumab and/or vemurafenib, a report should be completed and expeditiously submitted to Genentech, Inc. Follow-up to obtain the outcome of the pregnancy should also occur. Abortion, whether accidental, therapeutic, or spontaneous, should always be classified as serious, and expeditiously reported as an SAE. Similarly, any congenital anomaly/birth defect in a child born to a female subject exposed to atezolizumab and/or tiragolumab should be reported as an SAE.

- **Pregnancies in Female Partners of Male Patients**

Male patients will be instructed through the Informed Consent Form to immediately inform the investigator if their partner becomes pregnant during the study or within 30 days after the last dose of study drug.

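### Contraception after the last dose is 6 months in the eligibility criteria but 5 months in Section 9.8, and the pregnancy-notification text in Section 10.83 f does not fit the sections around it

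*Combined protocol and SAP*

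**What the plan says.** **Contraception period.** Criterion 3.39b (Section 3.3) asks persons of childbearing potential for abstinence or a method with a failure rate below 1% "per year during the treatment period and for 6 months after the last dose of study treatment". Criterion 3.39c asks persons able to father a child for abstinence or contraception, and for "agreement to refrain from donating sperm during the treatment period and for 6 months after the last dose of study treatment".

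Section 9.8 asks female and male patients of reproductive potential to avoid conception on study drug and "for 5 months after the last dose of study drug by complying with one of the following". Its closing paragraph repeats the figure as a condition of participation for patients of childbearing potential: "throughout the study period up to 5 months after the last dose of trial therapy".

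**Pregnancy notification.** Section 10.83 f gives three windows:

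- a female subject, vemurafenib and/or cobimetinib: "within 90 days after the last dose of vemurafenib and/or cobimetinib";
- a female subject, atezolizumab and/or tiragolumab and/or vemurafenib: 5 months after the last dose;
- the partner of a male patient: during the study or "within 30 days after the last dose of study drug", an instruction that is to reach the patient through the consent form.

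Three other places also bear on partner pregnancies. Section 9.9a requires that site staff be told at once and that the pregnancy be reported and followed, with no end date. Section 10.83 g extends reporting past the 30-day adverse-event period to partner pregnancies judged attributable to earlier atezolizumab and/or tiragolumab. Section 10.84 lists them among the reports sent to the drug supplier, with no cutoff after the last dose.

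**The concern.** Sections 3.3 and 9.8 both state conditions of entry, for the same people and the same interval, and they give different lengths. A site that counsels from 9.8, the section devoted to contraception, would give a shorter period than the one its patient had to agree to at registration. This also bears on eligibility. Section 13.5 treats as ineligible anyone who did not meet every criterion at registration and requires protocol treatment to stop, so a registration based on a 5-month agreement would satisfy 9.8 and fail 3.39b.

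The notification text raises a related safety question. Section 9.8 restricts conception by male patients partly because effects on sperm are unknown, yet the one notification instruction addressed to those men in 10.83 f ends well before either contraception period. If sites work from that sentence alone, some pregnancies conceived inside the contraception period may go unreported.

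**Working it through.** The plan gives no derived figure to reproduce. The check sets the stated durations side by side. For intervals in days, one month is taken as 365.25 / 12 = 30.44 days, so 5 months is 152.2 days and 6 months is 182.6 days.

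| Place | Who | Period after last dose |
|---|---|---|
| 3.39b | persons of childbearing potential | 6 months |
| 3.39c | persons able to father a child | 6 months |
| 9.8, main requirement | female and male patients | 5 months |
| 9.8, closing paragraph | patients of childbearing potential | 5 months |
| 10.83 f | female subject, vemurafenib and/or cobimetinib | 90 days |
| 10.83 f | female subject, atezolizumab and/or tiragolumab and/or vemurafenib | 5 months |
| 10.83 f | partner of a male patient | 30 days |
| 9.9a | partner of a male patient | no end date |
| 10.83 g | partner of a male patient, if attributed to atezolizumab and/or tiragolumab | after the 30-day period, no end date |

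**Step 1: contraception.** 6 − 5 = 1 month. Arm, drug and sex do not explain it: neither section distinguishes arms or drugs, and both address women and men. The 5-month figure stands twice in 9.8, so a single slip is an unlikely explanation.

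**Step 2: the 30-day partner instruction.** It ends 152.2 − 30 = 122.2 days before the 5-month period and 182.6 − 30 = 152.6 days before the 6-month period. It covers 30 / 152.2 = 20% of the one and 30 / 182.6 = 16% of the other. These figures describe that sentence of 10.83 f only, since 9.9a, 10.83 g and 10.84 also apply.

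**Step 3: vemurafenib.** It is named under both 90 days and 5 months, and the two differ by 152.2 − 90 = 62.2 days. In Section 7.11, Arm A's first cycle contains no atezolizumab, so the ambiguity matters chiefly for a patient who stopped in that cycle. For most others, the 5-month atezolizumab window also applies.

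**Step 4: where the text agrees.** The 5-month atezolizumab and tiragolumab reporting window equals the 9.8 period. It is one month shorter than the eligibility period.

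**Step 5: cross-reference.** Appendix III (Permitted Therapy) sends the reader to Section 9.7 for contraception. Section 9.7 covers atezolizumab/tiragolumab side effects; contraception is in 9.8.

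**The case against.** Several points on the other side are sound.

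- The contraception conflict runs one way. A patient who keeps to 6 months meets both sections.
- For men, 3.39c can be read so that the 6 months attaches only to sperm donation. The more natural reading covers both undertakings, and the conflict for persons of childbearing potential does not depend on it.
- Reporting windows and contraception periods serve different purposes and need not be equal. A difference between them is not in itself an error.
- Arms A and B are closed to enrollment, so the vemurafenib double listing cannot affect new registrations. The 6-versus-5-month conflict still reaches Arm C.

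A reader might infer that partner pregnancies are reportable only within 30 days and that fetal-exposure data are therefore lost. The documents do not support that. Section 9.9a requires immediate notice with no end date, 10.84 lists partner pregnancies without a cutoff, and 10.83 g reaches later ones. What stands is narrower. The sections do not agree: 9.9a opens with pregnancies arising on treatment, so its reach into follow-up is unclear, and 10.83 g depends on attribution and names neither vemurafenib nor cobimetinib.

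A reader might also count the note in Section 10.51, "within 120 days of completing the study", as one more conflicting window. It is not part of this point. It applies only if the protocol and the consent form lack certain wording on pregnancy, and it runs from study completion rather than from the last dose.

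Finally, a reader might conclude that patients are being given contradictory instructions. The consent pages are not available, so this cannot be checked. The conflict shown lies between sections of the protocol.

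**Conclusion.** The contraception conflict is established: 6 months in 3.39b and 3.39c against 5 months in 9.8, a one-month difference for patients of reproductive potential in every arm, with no rule of precedence. The consequence is a possible one-month shortfall against the eligibility agreement when a site works from 9.8 alone.

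The notification problem is established as an inconsistency between 10.83 f, 9.9a and 10.83 g, together with two windows for vemurafenib. That pregnancies may be missed is a reasonable risk to infer from the text; that they would be missed is not shown.

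The conclusion assumes that 3.39c's 6 months covers contraception as well as sperm donation (needed only for the male part), and that no arm- or drug-specific limit was intended but left unwritten. Endpoints, estimates and sample size are untouched. The point deserves correction because it concerns fetal exposure and the remedy is inexpensive.

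**What to change.** The sponsor's clinical and safety team should:

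1. reconcile 3.39b, 3.39c and both statements in 9.8 to one stated contraception period, and make clear in 3.39c which undertakings the period covers;
2. reconcile the partner-pregnancy instruction in 10.83 f with 9.9a and 10.83 g, so that a site can tell which duty applies and until when;
3. resolve the listing of vemurafenib under two reporting windows in 10.83 f;
4. correct the Appendix III cross-reference from 9.7 to 9.8;
5. check that the consent form agrees with the reconciled text.

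No duration is proposed here for contraception or for notification; both are for that team to decide. The cost is amended protocol wording, consent wording if the check shows it is needed, and the usual IRB approval. No data already collected and no planned analysis change.

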#### 9.9a Use in Pregnancy and Nursing

If a patient inadvertently becomes pregnant while on treatment on this study, the patient will immediately be removed from the study. The site will contact the patient at least monthly and document the patient's status until the pregnancy has been completed or terminated. The outcome of the pregnancy will be reported to Mayo Clinic without delay and within 24 hours to Mayo Clinic if the outcome is a serious adverse experience (e.g., death, abortion, congenital anomaly, or other disabling or life-threatening complication to the mother or newborn).

The study investigator will make every effort to obtain permission to follow the outcome of the pregnancy and report the condition of the fetus or newborn. If a male subject impregnates his female partner the study personnel at the site must be informed immediately and the pregnancy reported to Mayo Clinic and followed as described above.

Since many drugs are excreted in human milk, and because of the potential for serious adverse reactions in the nursing infant, patients who are breast-feeding are not eligible for enrollment

## 10.0 Adverse Event (AE) Monitoring and Reporting

The site principal investigator is responsible for reporting any/all serious adverse events to the sponsor as described within the protocol, regardless of attribution to study agent or treatment procedure.

The sponsor/sponsor-investigator is responsible for notifying FDA and all participating investigators in a written safety report of any of the following:

Any suspected adverse reaction that is both serious and unexpected.

- Any findings from laboratory animal or *in vitro* testing that suggest a significant risk for human subjects, including reports of mutagenicity, teratogenicity, or carcinogenicity.
- Any findings from epidemiological studies, pooled analysis of multiple studies, or clinical studies, whether or not conducted under an IND and whether or not conducted by the sponsor, that suggest a significant risk in humans exposed to the drug
- Any clinically important increase in the rate of a serious suspected adverse reaction over the rate stated in the protocol or Investigator's Brochure (IB).

**Summary of SAE Reporting for this study**  
(please read entire section for specific instructions):

WHO:	WHAT form:	WHERE to send:
All sites	Pregnancy Reporting [REDACTED]	Genentech: [REDACTED] Mayo Sites – attach to MCCC Electronic SAE Reporting Form Non Mayo sites – complete and forward to [REDACTED]
Mayo Clinic Sites	Mayo Clinic Cancer Center SAE Reporting Form [REDACTED] AND attach MedWatch 3500A: [REDACTED]	[REDACTED] [REDACTED]
Non-Mayo Clinic Sites	MedWatch 3500A: [REDACTED]	Genentech: [REDACTED] [REDACTED] [REDACTED]

## **Definitions**

### *Adverse Event*

Any untoward medical occurrence associated with the use of a drug in humans, whether or not considered drug related.

### *Suspected Adverse Reaction*

Any adverse event for which there is a reasonable possibility that the drug caused the adverse event.

### *Expedited Reporting*

Events reported to sponsor within 24 hours, 5 days or 10 days of study team becoming aware of the event.

### *Routine Reporting*

Events reported to sponsor via case report forms

### *Events of Interest*

Events that would not typically be considered to meet the criteria for expedited reporting, but that for a specific protocol are being reported via expedited means in order to facilitate the review of safety data (may be requested by the FDA or the sponsor).

### *Unanticipated Adverse Device Event (UADE)*

Any serious adverse effect on health or safety or any life-threatening problem or death caused by, or associated with, a device, if that effect, problem, or death was not previously identified in nature, severity, or degree of incidence in the investigational plan or application (including a supplementary plan or application), or any other unanticipated serious problem associated with a device that relates to the rights, safety, or welfare of subjects

## 10.1 Adverse Event Characteristics

**CTCAE term (AE description) and grade:** The descriptions and grading scales found in the revised NCI Common Terminology Criteria for Adverse Events (CTCAE) version 4.0 will be utilized for AE reporting. All appropriate treatment areas should have access to a copy of the CTCAE version 4.0. A copy of the CTCAE version 4.0 can be downloaded from the CTEP web site:

- 
- a. Identify the grade and severity of the event using the CTCAE version 4.0.
  - b. Determine whether the event is expected or unexpected (see Section 10.2).
  - c. Determine if the adverse event is related to the study intervention (agent, treatment or procedure) (see Section 10.3).
  - d. Determine whether the event must be reported as an expedited report. If yes, determine the timeframe/mechanism (see Section 10.4).
  - e. Determine if other reporting is required (see Section 10.5).
  - f. Note: All AEs reported via expedited mechanisms must also be reported via the routine data reporting mechanisms defined by the protocol (see Sections 10.6 and 18.0).

NOTE: A severe AE is NOT the same as a serious AE, which is defined in Section 10.4.

## 10.2 Expected vs. Unexpected Events

*Expected events* - are those described within the Section 15.0 of the protocol, the study specific consent form, package insert (if applicable), and/or the investigator brochure, (if an investigator brochure is not required, otherwise described in the general investigational plan).

*Unexpected adverse events* or suspected adverse reactions are those not listed in Section 15.0 of the protocol, the study specific consent form, package insert (if applicable), or in the investigator brochure (or are not listed at the specificity or severity that has been observed); if an investigator brochure is not required or available, is not consistent with the risk information described in the general investigational plan.

*Unexpected* also refers to adverse events or suspected adverse reactions that are mentioned in the investigator brochure as occurring with a class of drugs but have not been observed with the drug under investigation.

An investigational agent/intervention might exacerbate the expected AEs associated with a commercial agent. Therefore, if an expected AE (for the commercial agent) occurs with a higher degree of severity or specificity, expedited reporting is required.

NOTE: \*The consent form may contain study specific information at the discretion of the Principal Investigator; it is possible that this information may NOT be included in the protocol or the investigator brochure. Refer to protocol or IB for reporting needs.

